7.2.2. Exclusion criteria

For the **characteristics cohort**, patients meeting any of the following criteria will be excluded from the study:

- Prevalent mRCC patients (i.e. diagnosis of metastatic RCC before 1.1.2010)
- Prevalent RCC patients (i.e. diagnosis of RCC before 1.1.2010) if there is no records of metastatic disease during 2010-2021

For the **mRCC cohort**, patients meeting any of the following criteria will be excluded from the study:

- Prevalent patients with mRCC (i.e. diagnosis of metastatic RCC before 1.1.2010)
 - Note that patients with local RCC before 2010 are included in this study if the disease has metastasised during 2010-2021
- Patients without treatment for mRCC (see Table 3 for details)

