5. RATIONALE AND BACKGROUND

Renal cell carcinoma (RCC) is among the 10 most frequently occurring cancers and the most common type of kidney cancer occurring in Western communities [1]. RCCs comprise a heterogeneous group of malignant neoplasms arising from the nephron. Risk factors for RCC include obesity, hypertension, cigarette smoking, diet, diabetes, and male gender [1].

After decades of increasing trends in RCC incidence and mortality rates, it seems that rates are stabilising or starting to decline in many Western countries [1]. The worldwide number of kidney cancer cases was 431,288 (62.9% male) and deaths 179,368 (64.4% male) in 2020 [2]. Kidney cancer is more common in males compared to females. The incidence was 7.8 and mortality 3.0 per 100,000 males in high human development index countries in 2020 [2]. In Finland, the number of new kidney cancer cases was 635 in males and 353 in females in 2019 [3], and the number of prevalent patients was 4,943 males and 3,867 females in 2019 according to the Finnish Cancer Registry [4].

Localized RCC can be curatively treated with nephrectomy. However, about 20–30% of patients present with metastatic RCC (mRCC) at the time of diagnosis [5]. In addition, another 20% of patients with localized RCC undergoing nephrectomy will have a relapse and develop mRCC during follow-up. Despite the recent advances in mRCC treatment, metastatic disease is often fatal [6].

[figure not shown]
Over the last decade, the treatment of advanced/metastatic RCC has been constantly evolving, especially in the last 2-3 years with the emergence of several novel treatment options in rapid succession. Current recommendations for first-line therapy of mRCC include several combination treatments, superseding the previously recommended antiangiogenic agent monotherapies. The novel options combine an anti-PD-1-antibody with either an antiangiogenic drug (vascular endothelial growth factor receptor (VEGFR) tyrosine kinase inhibitor (TKI)), or an anti-CTLA-4-antibody. The combination treatments are recommended

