variably according to the patient's IMDC (International mRCC Database Consortium) risk score. IMDC represents a large collection of real-world data (RWD) on patients with advanced kidney cancer treated with targeted therapies [7,8]. IMDC combinations available for favourable risk patients include pembrolizumab + axitinib, nivolumab + cabozantinib and pembrolizumab + lenvatinib; for intermediate or poor risk patients the combination of ipilimumab and nivolumab is recommended in addition to the aforementioned three combinations. None of the recommended first-line treatment options have been compared head-to-head but all of the pivotal clinical studies have sunitinib monotherapy as a control, a former standard-of-care (SoC). The current second and later line treatment recommendations include VEGFR-TKI monotherapies, such as pazopanib and sunitinib, but will likely be reshaped in the coming years as clinical evidence on the optimal treatment sequence is accumulated.

The prognostic model constructed by the IMDC has been used to stratify patients in contemporary clinical trials and to provide risk-directed treatment selection in everyday clinical practice. The IMDC prognostic model contains six independent predictors of poor survival, which are: Karnofsky performance status of less than 80%, less than 1 year from diagnosis to treatment, anaemia (haemoglobin concentration <lower limit of normal), hypercalcaemia (corrected calcium concentration >upper limit of normal), neutrophilia (neutrophil count >upper limit of normal), and thrombocytosis (platelet count >upper limit of normal). An IMDC risk score is determined for a patient according to the number of poor prognostic factors the patient has; favourable risk patients have 0 factors; intermediate risk patients have one or two factors; and poor risk patients have three or more factors.

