- Treatment initiation for mRCC (sunitinib, pazopanib, cabozantinib, ipilimumab, nivolumab)

When analyzing the treatment outcomes, index is defined as the date of the treatment initiation.

End of follow-up (whichever of the following occurs first):

- Death
- Moving outside of HDSF
 - Approximated using data of healthcare contacts; no contacts to specialty care of HDSF within 2 years (patient censored at the last recorded visit)
- End of study (31.12.2021)

Length of follow-up (in years): ('end of follow-up' – 'index' + 1)/365.25

Definitions for characteristics cohort

Index:

- For mRCC patients, same as for the mRCC cohort (i.e. approximated metastasis date)
- For RCC patients, the date of the first record of RCC diagnosis (ICD-10: C64)

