7.3. Variables

Source for all variables is the data lake of HDSF.

Table 2. List of study variables. Abbreviations: PO=primary objective, SO=secondary objective.

Variable	Role/Relevant objective	Operational definition
ICD-10 diagnoses; RCC diagnoses	Patient inclusion/exclusion IMDC risk category	yes/no
ICD-10 diagnoses: co-diagnoses (e.g. renal insufficiency and hypertension)	PO1, SO1	yes/no; co-diagnoses before and after index
Date of birth	Patient inclusion PO1	Date; age defined at index based on birth date
Date of death	End of follow-up PO3	Date
Gender	PO1	Female/male
Home municipality	Patient inclusion End of follow-up	Home municipality at each healthcare contact
Weight	PO1	kg
Height	PO1	m
Body mass index (BMI)	PO1	derived from weight and height
Smoking status (if available in structured format)	PO1	yes/no
Outpatient visits (including emergency room visits)	Patient inclusion and index definition (visits to oncologist) SO2	Date, physician's specialty, type of arrival
Hospitalizations	SO2	Start and end dates
Procedures and operations (including nephrectomy)	PO1 SO1 SO2	Procedure code, date
Medical imaging	SO1 SO2	Imaging code, date
Medications; including - hospital medications - prescriptions	Patient inclusion/exclusion and index definition PO2 PO3 SO1 SO2	Dates, ATC-codes, active substance
Laboratory testing	IMDC risk category PO1	Dates, test id, result
Zubrod/ECOG performance status	IMDC risk category PO1	scale 0-5; converted to Karnofsky
PAD histology (if available in structured format)	PO1	
Staging of RCC, the tumor-node-metastasis (TNM) classification	Patient inclusion and index definition PO1	scale 1-4 (stages)

PFIZER CONFIDENTIAL

Table 3. List of medications for RCC treatment. ATC= Anatomical Therapeutic Chemical.

	Active substance	Brand name	ATC-code at the moment in use	ATC-code previously in use
Oral medications	axitinib	Inlyta	L01EK01	L01XE17
	everolimus	Afinitor	L01EG02	L01XE10
	cabozantinib	Cabometyx	L01EX07	L01XE26
	pazopanib	Votrient	L01EX03	L01XE11
	sorafenib	Nexavar	L01EX02	L01XE05
	sunitinib	Sutent	L01EX01	L01XE04
Intravenous medications	ipilimumab	Yervoy	L01XC11	
	nivolumab	Opdivo	L01XC17	

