7.7.1. Patient characteristics

[figure not shown]
Primary objective 1:

Demographical and clinical variables of RCC and mRCC patients will be summarized at index. Treated and non-treated mRCC patients will be analysed separately. For laboratory measures and performance status, the closest available measure +/- 90 days from index will be utilized. In case of a high rate of missing values, the time window can be extended to 6 months.

The demographical and clinical variables include but are not limited to:

- age at index
- sex
- history of renal insufficiency (any records until index)
 - ICD-10 code: N17-N19
- history of dialysis (any records until index)
 - procedure codes: TK800, TK829, TK810,
 - ICD-10 code: Z49

PFIZER CONFIDENTIAL

- history of kidney transplant (any records until index)
 - procedure codes: KAS10, KAS20
 - ICD-10 code: Z94.0
- history of nephrectomy (any records until index)
 - procedure codes: KAC*, KAD*, KAS40, KAS41
 - ICD-10 code: Z90.5
- performance status at index
 - Karnofsky (converted from Zubrod/ECOG)
- time from initial diagnosis of RCC to initiation of treatment for metastatic RCC
- various laboratory measures (e.g. hemoglobin, serum calcium, neutrophiles, thrombocytes, creatinine, albumin, eGFR)
- smoking status (if available in structured format)
- histology (if available in structured format)
- BMI (if available in structured format)

For categorical variables, the number (N) and the proportion (%) of patients in each class will be reported. For continuous normally distributed variables, mean and standard deviation (SD) will be reported. For continuous, non-normally distributed variables, median, the 1st quartile and the 3rd quartile will be reported.

The difference between strata will be tested using chi-squared/Fisher's exact test (categorical variables), t-test (continuous normally distributed variables) and Kruskal-Wallis test (continuous non-normally distributed variables).

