7.7.2. Treatment patterns and treatment lines

Primary objective 2:

The treatment lines will be defined using drug administration and prescription data. The treatment options and lines will be visualized using Sankey plots and the proportion of patients per treatment type will be reported.

In general in mRCC, line of treatment (LOT) changes when the active substance changes, as the treatments are mainly monotherapies and only a few options consist of two substances (e.g. combination of ipilimumab and nivolumab in 1L).

The treatment lines will be defined *post hoc* using following process:

- For each active substance, single administrations/prescriptions are merged to treatment continuums.
- To identify, whether the treatment is monotherapy or combination of two active substances, the first records of the active substances will be considered

- if the first records of the two active substances are within 28 days, the treatment is considered as combination therapy of these two medications
- otherwise the two active substances are considered as two separate treatment lines
- The initiation of the treatment line is defined as the date of first record (dosing or prescription) of the active substance.

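### The drug list that defines treated mRCC omits pembrolizumab and lenvatinib, so a patient given only that pair is classed as non-treated

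*Combined protocol and SAP*

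**What the plan says.** Section 7.2.2 excludes from the mRCC cohort "Patients without treatment for mRCC (see Table 3 for details". The list it points to is "Table 3. List of medications for RCC treatment" in section 7.3. It has eight substances: axitinib, everolimus, cabozantinib, pazopanib, sorafenib, sunitinib, ipilimumab and nivolumab. Nothing marks the list as open-ended, whereas sections 7.7.1 and 7.7.6 say explicitly when their lists are not exhaustive.

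Section 5 names four first-line combinations. Three are given as "pembrolizumab + axitinib, nivolumab + cabozantinib and pembrolizumab + lenvatinib"; the fourth is ipilimumab with nivolumab.

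Treated status is used twice. For primary objective 1, section 7.7.1 says: "Treated and non-treated mRCC patients will be analysed separately". Section 6 restricts all other objectives to treated mRCC patients.

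Two other places also depend on which drugs count:

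- The index definition in section 7.2 has its own, shorter list: "Treatment initiation for mRCC (sunitinib, pazopanib, cabozantinib, ipilimumab, nivolumab".
- Section 7.7.2 builds treatment lines as follows: "For each active substance, single administrations/prescriptions are merged to treatment continuums". It does not say whether this covers Table 3 drugs only or every recorded anticancer drug.

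**The concern.** A list that decides who is treated should cover every drug the protocol itself regards as treatment for the disease, or explain the gaps. Table 3 does neither for pembrolizumab and lenvatinib.

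The omission affects entry to the main cohort. Misclassified patients would enlarge and distort the non-treated group in primary objective 1 and be absent from treatment patterns, survival, time to next treatment (TTNT), morbidity and resource use.

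Any loss would not be spread evenly over calendar time. Section 5 describes treatment as changing "especially in the last 2-3 years with the emergence of several novel treatment options in rapid succession", so missing patients would fall mainly at the end of the 2010-2021 window. The study information page says that treatment sequence and outcomes will be examined over time, and diagnosis year is a Cox covariate in section 7.7.3.

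**Working it through.** **1. The plan's own size figure (section 7.5).** 1,100 RCC patients × 20% = 220, and 1,100 × 50% = 550. The stated 220-550 mRCC patients is reproduced. The classification problem does not depend on it.

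**2. Section 5 combinations against the two drug lists.**

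| Combination (section 5) | Components in Table 3 | Components in section 7.2 index list |
|---|---|---|
| nivolumab + cabozantinib | 2 of 2 | 2 of 2 |
| ipilimumab + nivolumab | 2 of 2 | 2 of 2 |
| pembrolizumab + axitinib | 1 of 2 (axitinib) | 0 of 2 |
| pembrolizumab + lenvatinib | 0 of 2 | 0 of 2 |

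Two combinations are fully listed in Table 3, one is half listed and one is absent.

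**3. What follows directly.** A patient whose only mRCC drugs are pembrolizumab and lenvatinib has no Table 3 record. Section 7.2.2 then makes that patient non-treated, whatever brought the patient into the mRCC population. A pembrolizumab + axitinib patient is still treated, through axitinib.

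**4. What is conditional.** If section 7.7.2 is applied to Table 3 drugs only:

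- pembrolizumab + axitinib is recorded as axitinib alone;
- a switch to an unlisted drug is not a TTNT event;
- after an unlisted first line, line 1 starts too late. The date for the IMDC category moves with it, which affects the under-one-year factor and the ±3-month window for performance status and laboratory values.

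If all anticancer records are used, none of these three effects occurs.

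**5. The two lists against each other.** Table 3 has 8 drugs and the section 7.2 index trigger has 5. Axitinib, everolimus and sorafenib are in Table 3 but not in the trigger. The effect is probably small: the index is the earliest of four triggers, and section 7.2.1 expects an oncologist visit when disease metastasises, so another trigger will usually set the date.

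**6. Scale, for illustration only.** The documents give no usage figures. Take the last 2-3 years in section 5 as counted back from the protocol date, 28 March 2022:

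- 28.3.2020 to 31.12.2021 = 644 days = 1.76 years; 644 / 4,383 study days = 14.7%.
- 28.3.2019 to 31.12.2021 = 1,010 days = 2.77 years; 1,010 / 4,383 = 23.0%.
- With even accrual (assumed), the lowest count is 14.7% × 220 = 32 patients with an index date in that period and the highest is 23.0% × 550 = 127.

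| Assumed share receiving only unlisted drugs | Patients misclassified |
|---|---|
| 0% | 0 |
| 5% | about 2 to 6 |
| 10% | about 3 to 13 |

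This is not an upper bound. Section 7.2.2 also admits patients with local RCC before 2010 who metastasised later, and they are outside the 220-550 base. Patients with an earlier index may also start treatment in this period.

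**The case against.** The best defence is that Table 3 reflects what was actually used locally. Section 5 reports recommendations current in March 2022, while data end on 31.12.2021. It also says that Finnish treatment was shaped by reimbursement and that combinations are often problematic. Section 7.7.2 describes treatment as mainly monotherapy. The certain effect requires a patient with no Table 3 drug in any line, and there may be none. The line, TTNT and IMDC effects are conditional. Recent patients would have short follow-up and add little to survival estimates. Sections 7.8 and 7.9 provide for clinical review of results and of line construction.

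Much of this stands as a limit on size: the number may be zero, the downstream effects depend on an unstated choice, and the 5% and 10% shares have no support in the documents. It does not remove the defect. The protocol never gives local non-use as the reason for the omission, so a reader could not tell no use from use that was not counted. Short follow-up matters little for the treated/non-treated split or for treatment patterns. A plausibility review may reveal oddly untreated patients, but it does not change the list that defines treated.

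**Conclusion.** The concern holds. As written, the exclusion rule misclassifies any patient treated only with pembrolizumab + lenvatinib, a combination that the protocol itself names as first-line treatment. This follows from the text and needs no assumption about use.

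The size is unknown and possibly zero. The illustrative counts rest on assumed even accrual and assumed shares, and they carry no weight in the conclusion. The effects on lines, TTNT and IMDC category hold only if line construction is limited to Table 3. The mismatch between the five-drug and eight-drug lists is secondary.

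The point should be fixed before analysis because the definition controls entry to every objective except the first, any loss would cluster in the latest years, and the correction is cheap.

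**What to change.** Use one ATC-coded drug list: Table 3 plus pembrolizumab and lenvatinib. Cite it for the index trigger, the inclusion criterion, treated status, outcome time zero, the IMDC date and line construction, so that sections 7.2, 7.2.1, 7.2.2, 7.2.3, 7.7.2 and 7.7.3 agree. If the two drugs are left out on purpose, for example because there was no use in HDSF in 2010-2021, say so in one sentence.

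Report how many mRCC patients have other ATC L01 records outside the list. All 14 codes in Table 3 (8 current, 6 earlier) begin with L01. Table 2 records no indication for medications, so some of these records may relate to another cancer; the count is a check on completeness and should not be used to reclassify patients.

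The cost is definition text and no extra patients. Table 2 already collects hospital medications and prescriptions with "Dates, ATC-codes, active substance". The one practical step is to confirm that the extract includes the two drugs. If the data request to Auria Clinical Informatics was limited to Table 3 codes, it would need extending, and section 4 allows one month for data collection, so this should be checked first.

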6. RESEARCH QUESTION AND OBJECTIVES

The objective of this study is to describe the characteristics and treatment outcomes of patients with advanced/metastatic RCC with medical records in the HDSF data lake. In the first primary objective, all RCC patients (with local or metastatic disease) are analyzed (treated and non-treated mRCC patients separately). In all other objectives, only treated mRCC patients will be analyzed. The objectives of the study are to:

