7.2.1. Inclusion criteria

For the **characteristics cohort**, patients must meet all of the following inclusion criteria to be eligible for inclusion:

- Diagnosis of renal cell carcinoma (ICD-10: C64) during 1.1.2010-31.12.2021
- Age at least 18 years at index.
- Resident of HDSF at index.

For the **mRCC cohort**, patients must meet the following inclusion criteria in addition to the above criteria to be eligible for inclusion:

- metastatic RCC during 1.1.2010-31.12.2021; defined as
 - ICD-10 diagnosis code for metastasis (C77*-C79*), or
 - AJCC stage 4, or
 - AJCC stage data potentially not available for all patients
 - a visit to oncologist (specialty code 65) with RCC as main diagnosis, or
 - In Finland, the ICD-10 codes for metastatic disease are rarely used. In contrast, RCC patients visit oncologist, when and only when disease metastasises and therefore, the visit can be used as a proxy to a metastatic disease.
 - initiation of treatment for mRCC

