7.5. Study size

The expected number of patients eligible for this study is approximated based on publicly available data from the Finnish Cancer registry (<https://syoparekisteri.fi/tilastot/tautitilastot/>):

- In HDSF, there have been approximately 1,100 RCC patients during 2010-2021.
- 20-50% of RCC patients develop advanced/metastatic disease [9] and therefore, the size of mRCC-patient cohort is approximately 220-550 patients.

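### Non-treated mRCC has no time window, so the descriptive non-treated column mixes patients who had not yet started a drug with patients observed for long, or until death, without one

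*Combined protocol and SAP*

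**What the plan says.** Section 7.2.2 excludes from the mRCC cohort "Patients without treatment for mRCC (see Table 3 for details". Table 3 lists eight drugs. Neither place says by when a drug must have been recorded, and the protocol gives no other definition of non-treated.

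Section 7.2.1 admits "metastatic RCC during 1.1.2010-31.12.2021; defined as" a metastasis code, AJCC stage 4, an oncologist visit or treatment initiation. Section 7.2 ends follow-up at the earliest of death, "End of study (31.12.2021") and a proxy for moving away: "no contacts to specialty care of HDSF within 2 years (patient censored at the last recorded visit"). For the characteristics cohort, the index is "For mRCC patients, same as for the mRCC cohort (i.e. approximated metastasis date"), so treated status is decided by what happens after index.

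The status is used twice. In section 7.7.1, for primary objective 1, "Treated and non-treated mRCC patients will be analysed separately". Section 6 adds: "In all other objectives, only treated mRCC patients will be analyzed". No section sets a minimum observation time after index. The limitations in section 7.9 cover missing data and misclassified treatment lines, but not this point.

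**The concern.** The time available to become treated depends on the calendar. A patient indexed in November 2021 has at most about two months in which a drug start can be seen. A patient indexed in 2012 has up to nine years or more. Two patients with the same course can therefore land in different columns only because of when metastatic disease was recorded.

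The non-treated column then answers no single question. It holds patients who died without a drug, patients followed for years without one, and patients for whom the data simply stopped too early. A reader of primary objective 1 will take it as a description of patients who do not receive drug treatment. The same rule leaves the treated cohort with mainly early starters among the most recent index dates.

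**Working it through.** **The plan's own figure.** Section 7.5 states "In HDSF, there have been approximately 1,100 RCC patients during 2010-2021" and that 20-50% develop advanced or metastatic disease. 1,100 × 0.20 = 220 and 1,100 × 0.50 = 550, so the stated 220-550 reproduces. It derives from all metastatic disease, so I take it as treated plus non-treated mRCC.

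**Potential observation.** The identification window is 12 years, T = 144 months. Assuming uniform index dates, 12/144 = 8.3% of patients (18-46) have 12 months or less before the cut-off, and 3/144 = 2.1% (5-11) have 3 months or less.

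**Assumptions; none of these is in the protocol.** 60-75% of mRCC patients eventually start a Table 3 drug. The lag from index to first drug is exponential with mean 2 months, except for 0-25% of eventual starters, whose mean lag is 12-24 months. Observation is cut only at 31.12.2021.

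**Formula.** For mean lag m and index dates uniform over T months, the share of eventual starters not yet started at the cut-off is f(m,T) = (m/T)(1 − exp(−T/m)).

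| m (months) | f(m,144), all years | f(m,12), 2021 index |
|---|---|---|
| 2 | 0.0139 | 0.166 |
| 12 | 0.0833 | 0.632 |
| 24 | 0.1663 | 0.787 |

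With slow share s, F = (1 − s)·f(2,T) + s·f(m,T). With proportion p eventually treated, the not-yet-treated share of the non-treated column is pF/(1 − p + pF).

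| p | s | m slow | F, all years | Patients, N=220 / N=550 | Share of column |
|---|---|---|---|---|---|
| 0.60 | 0 | – | 0.0139 | 1.8 / 4.6 | 2.0% |
| 0.75 | 0 | – | 0.0139 | 2.3 / 5.7 | 4.0% |
| 0.60 | 0.25 | 12 | 0.0312 | 4.1 / 10.3 | 4.5% |
| 0.75 | 0.25 | 12 | 0.0312 | 5.2 / 12.9 | 8.6% |
| 0.60 | 0.25 | 24 | 0.0520 | 6.9 / 17.2 | 7.2% |
| 0.75 | 0.25 | 24 | 0.0520 | 8.6 / 21.4 | 13.5% |

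**Index in 2021.** With no slow starters, F = 0.166, so about 17% of eventual starters are labelled non-treated. With 25% slow starters it is 0.75 × 0.166 + 0.25 × 0.632 = 28% (m = 12) or 0.75 × 0.166 + 0.25 × 0.787 = 32% (m = 24).

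**Concentration.** The 2021 index dates supply (1/12)·F(12)/F(144) of all not-yet-treated patients: nearly all with no slow starters, 75% with m = 12 and 52% with m = 24.

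**Treated patients indexed in 2021.** If 25% of eventual starters are slow, they make up 0.25 × 0.368/0.717 = 13% (m = 12) or 0.25 × 0.213/0.679 = 8% (m = 24) of those already treated.

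**Sensitivity to the lag model.** With one exponential lag for everyone, median 2 to 12 months and 50-80% eventually treated, the share of the column runs from 2.0% to 32.5%. The top needs a 12-month median for all starters. That is hard to square with an index that may itself be the drug start, where the lag is zero.

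**The case against.** *The cut-off is inferred.* Section 7.2.2 attaches no date. The end-of-follow-up rule stands under the definitions for the mRCC cohort, which holds treated patients only, and the characteristics cohort has only an index definition. Section 4 plans data collection for May 2022, and the protocol does not say whether a drug record from early 2022 would count. This stands: 31.12.2021 is the natural reading, not an explicit rule. It is also a reason to write the rule down.

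*No comparison depends on it.* A reader might infer that treated and non-treated patients are formally compared and that the comparison is biased. The text does not support that. Section 7.7.1 describes them separately and tests differences between strata, which section 7.2.3 lists as IMDC category and treatment line. Nor is a table of the non-treated share by calendar year planned, so a rising share in the last years would not be a reported result.

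*The effect is small.* If not-yet-treated patients resemble treated ones, 2-13.5% contamination shrinks an assumed 20-point difference by 0.4-2.7 points (20 × 0.02 to 20 × 0.135). For proportions near 50%, the standard error of that difference is √(0.25(1/330 + 1/220)) = 4.4 points (N=550, 60% treated) to √(0.25(1/165 + 1/55)) = 7.8 points (N=220, 75% treated). Every lag input is assumed, and shares above 4% need slow starters. This stands for the whole column; it does not stand for the 2021 index dates.

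*The outcome analyses are protected.* A reader might also infer that the survival results are invalid. That goes too far: by treatment line the clock starts at line initiation, and diagnosis year is a Cox covariate (section 7.7.3), which partly addresses calendar shift. The case mix of recent treated patients still differs.

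**Conclusion.** The point holds as a matter of definition. As written, non-treated means no Table 3 drug recorded while the patient could be observed, and nothing in the protocol separates not yet treated from long or fully observed without treatment.

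Under the assumptions above, about 2-13% of the non-treated column is not yet treated: roughly 2-9 patients if there are 220 with mRCC, and 5-21 if there are 550. With no slow starters it is 2-4%. Between about half and nearly all of these patients have 2021 index dates, where at least about 17% of eventual starters would be mislabelled. How many start late cannot be settled from the protocol; the data will show it.

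The consequence is a modestly blurred descriptive column in primary objective 1, plus a treated cohort whose recent members are mainly early starters. It is not a flawed test or an invalid outcome analysis. The change is worth making because it is cheap.

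**What to change.** In sections 7.2.2 and 7.7.1, name the group *no Table 3 drug recorded by end of follow-up*, and state that end of follow-up applies to the characteristics cohort too. Within the group, report separately:

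- (a) patients who died without a drug, or had at least 12 months of observation after index without one;
- (b) patients alive at 31.12.2021 with under 12 months of observation;
- (c) patients lost to contact within 12 months of index.

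Add the cumulative incidence of first drug from the mRCC index, with death as competing event. This also shows slow starters, whom a 12-month split does not fully catch: in the model with 25% slow starters, 25-48% of not-yet-treated patients have index dates before 2021 and would stay in (a).

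As a sensitivity analysis, repeat the treated and non-treated descriptions for index dates up to 31.12.2020. Under uniform accrual this leaves out 8.3% of patients (18-46) and keeps about 202-504; the main tables keep everyone.

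In section 7.9, state that treated patients with recent index dates are mainly early starters. These changes describe that shift but do not remove it.

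The cost is protocol wording, one extra derived variable and smaller subgroups. The medication, contact and death dates are already in Table 2.
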